15.2 Exceptions

The following situations shall not be reported as SAEs:

- ◆ Elective hospitalization for pre-existing conditions that have not been exacerbated by trial treatment.
- ◆ A hospitalization which was planned before the patient consented for study participation and where admission did not take longer than anticipated.
- ◆ A hospitalization planned for protocol related treatment or protocol related procedure as per institutional standard timelines. However, events requiring hospitalizations or prolongation of hospitalization as a result of a complication of therapy administration or clinical trial procedures will be reported as SAEs.
- ◆ Social, technical, administrative and/or convenience admission to a hospital, in absence of a SAE
- ◆ Medical or surgical procedure (e.g. endoscopy, appendectomy); the condition that leads to the procedure should be reported if meets the definition of an (S)AE. For example, an acute appendicitis that begins during the adverse event reporting period should be reported as the (S)AE, and the resulting appendectomy should be recorded as treatment of the AE. Situations where an untoward medical occurrence did not occur (palliative care, rehabilitation, overdose without occurrence of an adverse event).
- ◆ Anticipated day-to-day fluctuations of pre-existing disease(s) or condition(s) present or detected at the start of the study that do not worsen.
- ◆ An emergency visit due to an accident where the patient is treated and discharged.
- ◆ When the patient is held 24 hours for observation and finally is not admitted.

- ◆ Planned treatments at sites not associated to a hospital and generally considered as minor surgical procedures (i.e., laser eye surgery, arthroscopy, etc).

By EORTC convention, clinical events related to the primary cancer being studied or to the primary cancer progression are not to be reported as SAEs, even if they meet any of the seriousness criteria from the standard SAE definition (i.e. fatal, hospitalization, etc.),.,), **unless** the event is more severe than expected and therefore the investigator considers that their clinical significance deserves reporting.

15.3 Severity assessment

The severity of all AEs (serious and non-serious) in this trial should be graded using CTCAE v4.0
[www.eortc.org\investigators-area\ctc](http://www.eortc.org/investigators-area/ctc)

15.4 Causality assessment

The investigator is obligated to assess the relationship between protocol treatment and the occurrence of each SAE following the definitions in this table:

Relationship to the protocol treatment	Description
Reasonable possibility	There is a reasonable possibility that the protocol treatment caused the event
No reasonable possibility	There is no reasonable possibility that the protocol treatment caused the event

The investigator will use clinical judgment to determine the relationship. Alternative causes, such as natural history of the underlying diseases, medical history, concurrent conditions, concomitant therapy, other risk factors, and the temporal relationship of the event to the protocol treatment will be considered and investigated.

The decision will be recorded on the SAE form and if necessary the reason for the decision will also be recorded.

15.5 Expectedness assessment

The expectedness assessment is the responsibility of the sponsor of the study. The expectedness assessment will be performed against the following reference documents:

- ◆ Trabectedin: most updated Investigator's Brochure.
- ◆ Local standard of care treatment: Summary of Product Characteristics (SmPC).

If information on expectedness has been made available by the reporting investigator, this should be taken into consideration by the sponsor.

15.6 Reporting procedure for investigators

This procedure applies to all Serious Adverse Events (SAEs) occurring from the time a subject is randomized until 30 days after last protocol treatment administration, or until the start of a new antitumor therapy, whichever occurs first; and to any SAE that occurs outside of the SAE detection period (after the 30-days period), if it is considered to have a reasonable possibility to be related to the protocol treatment or study participation.

Randomization till 30 days after last protocol treatment administration, or until the start of a new antitumor therapy, whichever occurs first:	All SAEs
From day 31 after last protocol treatment administration (or after start the start of a new antitumor therapy):	Only related SAEs

Any secondary malignancy should also be reported in expedited way on a SAE form with the appropriate seriousness criteria!

All reporting must be done by the principal investigator or authorized staff member (i.e. on the signature list) to confirm the accuracy of the report.

All SAE data must be collected on the study-specific SAE form.

All SAEs must be reported immediately and no later than 24 hours from the time the investigator or staff became aware of the event.

All SAE-related information needs to be provided in English.

All additional documents in local language must be accompanied by a translation in English, or the relevant information must be summarized in a follow-up SAE report form.

All SAE-related information must be send to the EORTC Pharmacovigilance Unit:

EORTC Pharmacovigilance Unit:

[contact]

[contact]

To enable the Sponsor to comply with regulatory reporting requirements, all initial SAE reports should always include the following minimal information: an identifiable patient (SeqID), a suspect medicinal product if applicable, an identifiable reporting source, the description of the medical event and seriousness criteria, as well as the causality assessment by the investigator. Complete information requested on the SAE form of any reported serious adverse event must be returned within 7 calendar days of the initial report. If the completed form is not received within this deadline, the Pharmacovigilance Unit will make a written request to the investigator.

Queries sent out by the EORTC Pharmacovigilance Unit need to be answered within 7 calendar days.

The investigator must provide any relevant information as requested by the Sponsor in addition to that on the CRF.

All forms need to be dated and signed by the principal investigator or any authorized staff member (i.e. on the signature list).

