- ◆ No known MRI or CT, including contrast media, contraindications
- ◆ Absence of any psychological, familial, sociological or geographical condition potentially hampering compliance with the study protocol and follow-up schedule; those conditions should be discussed with the patient before registration in the trial
- ◆ Before patient randomization, written informed consent must be given according to ICH/GCP, and national/local regulations.

Important note: All eligibility criteria must be adhered to, in case of deviation discussion with Headquarters and study coordinator is mandatory.

4 Trial Design

This is a randomized open label multicenter comparative phase II trial. The Korn design (Ref. 10) will be applied (for detailed statistical considerations see chapter 8).

[figure not shown]
Patients will be randomized at the EORTC headquarters after verification of the eligibility criteria (see chapter 3) to receive one of the following:

- ◆ Arm 1 (treatment): Trabectedin delivered as a 24-hour infusion every 3 weeks (day 1 of each 21-day cycle) at a starting dose of 1.5 mg/m² body surface area (BSA), until one of the treatment withdrawal criteria has been met.
- ◆ Arm 2 (control): Local standard of care.

For the trabectedin arm one cycle will be defined as 3 weeks.

For the control arm one cycle will be defined according to the treatment schedule of the chosen drug.

Disease will be assessed by the Macdonald response criteria (see chapter 7).

5 Therapeutic regimens, expected toxicity, dose modifications

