5.6.1.2 Re-treatment criteria

- ◆ A maximum delay of 3 weeks from the due date for next infusion is allowed for recovery from toxicity in the preceding cycle of treatment.
- ◆ The following criteria should be met before the next infusion:

Hematological parameters	Value at day 1 of new treatment cycle
Hemoglobin	≥ 9 g/dL or ≥ 5.6 mmol/L
Platelet count	$\geq 100 \times 10^9$ /L
Neutrophil count	$\geq 1.5 \times 10^9$ /L
Serum chemistry parameters	Value at day 1 of new treatment cycle
Creatinine clearance	≥ 30 mL/min
Creatine phosphokinase	$\leq 2.5 \times$ ULN
Total bilirubin	\leq ULN
ALT or AST	$\leq 2.5 \times$ ULN
Alkaline phosphatase	$\leq 2.5 \times$ ULN
Albumin	≥ 25 g/L
Non hematological – non serum chemistry parameters	Status at day 1 of new treatment cycle
Severity of other adverse event has to recover to \leq Grade 1	

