5.6.1.3 Treatment discontinuation

In the event that more than two dose reductions are required or a delay of more than 3 weeks from the due date for next infusion are necessary, patient must go off protocol treatment.

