6.3 During treatment

The following need to be performed on day 1 of each treatment cycle or within 72 hours before:

- ◆ Clinical examination (WHO PS, blood pressure, pulse rate, body weight, and body temperature).
- ◆ Assessment of all adverse events that have occurred since the previous visit and ongoing events from previous cycles should be followed.
- ◆ Complete blood counts to include hemoglobin, white blood cells, neutrophils, lymphocytes, platelets. For the experimental arm only, additional monitoring of hematological values should occur weekly during the first two cycles of therapy, and at least once between treatments in subsequent cycles
- ◆ A serum chemistry assessment to include at least creatinine, total bilirubin, ALT, AST, ALP, CPK, albumin, LDH, sodium, potassium, glucose, calcium. For the experimental arm only, additional monitoring of serum chemistry values should occur weekly during the first two cycles of therapy, and at least once between treatments in subsequent cycles
 - ◆ If ALP > 2.5 ULN, ALP hepatic isoenzyme 5-nucleotidase and/or GGT tests must be performed; ALP hepatic isoenzyme or 5-nucleotidase and/or GGT must be within the normal range.
 - ◆ Creatinine clearance will be calculated by Cockcroft and Gault formula (see Appendix E)
 - ◆ For the serum chemistry parameters not collected on the Serum Chemistry form: in case of abnormal value please record it as adverse event on the Adverse Event forms (grade, relationship, seriousness).
- ◆ Cranial MRI every 9 weeks from randomization and if clinically indicated
- ◆ Recording of corticosteroid dose every 9 weeks
- ◆ CT thorax/abdomen only if clinically indicated; if tumorous or unclear lesions detected repeat CT every 9 weeks and if clinically indicated
- ◆ HRQoL: QLQ-C30 (v3) and the BN-20 questionnaire: regardless the treatment arm, at week 3, week 6 and week 12 after treatment start (for more information see chapter 10).
- ◆ Pregnancy test (every two cycles)

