7.2 Evaluation of safety

7.2.1 Adverse events

All adverse events will be recorded; the investigator will assess whether those events are drug related (reasonable possibility, no reasonable possibility) and this assessment will be recorded in the database for all adverse events.

Only the worst grade per CTCAE category will be recorded per cycle. The collection period will start from randomization up to 30 days after administration of the last dose of protocol treatment or until the start of a new antitumor therapy, whichever occurs first.

All adverse events must be followed until resolution or stabilization.

Whenever possible, the Investigator will record the main diagnosis instead of the signs and symptoms normally included in the diagnoses.

Investigators must pursue and obtain information adequate both to determine the outcome and to assess whether it meets the criteria for classification as a SAE requiring immediate notification.

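### AE and all-SAE collection ends 30 days after the last dose, but a trabectedin patient may wait 42 days, so up to 12 days on protocol are only partly covered

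*Combined protocol and SAP*

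**What the plan says.** **Collection window.** Section 15.6 applies SAE reporting "from the time a subject is randomized until 30 days after last protocol treatment administration", or to the start of new antitumor therapy if that comes first. It then adds "any SAE that occurs outside of the SAE detection period (after the 30-days period), if it is considered to have a reasonable possibility" of being related to protocol treatment or study participation, and gives no end date for this. The table in 15.6 says the same: from day 31, related SAEs only. For AEs, 7.2.1 states "The collection period will start from randomization up to 30 days after administration of the last dose of protocol treatment", with the same cut at new therapy and no exception for related events after the window. It also states "All adverse events must be followed until resolution or stabilization".

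**Permitted wait.** Chapter 4 defines the trabectedin cycle as 21 days. Section 5.6.1.2 states "A maximum delay of 3 weeks from the due date for next infusion is allowed for recovery from toxicity". Section 5.6.1.3 acts only once that limit is passed: if "a delay of more than 3 weeks from the due date for next infusion are necessary, patient must go off protocol treatment".

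**Visits and analysis.** On day 1 of each cycle (or within 72 hours before), 6.3 requires "Assessment of all adverse events that have occurred since the previous visit and ongoing events from previous cycles should be followed". The post-treatment visit in 6.4.1 is timed 30 days after the last administration and follows ongoing AEs. Section 6.4.3 also follows ongoing AEs. The summary table in 6.5 marks AE assessment as mandatory every 9 weeks until progression, without limiting it to ongoing events. Section 8.2.3.4 uses all forms up to the last safety assessment before progression or further therapy, and lists severe grades that first appear in follow-up.

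**The concern.** The collection window is anchored on the last dose, but which dose was the last is known only afterwards. A patient waiting to recover is still on protocol treatment. If the patient is re-dosed, the days of waiting fall inside the window. If the patient does not recover and comes off, the previous dose becomes the last one, and any waiting day after day 30 falls outside. The rule for the same calendar days therefore depends on how the wait ends, and a site at day 35 cannot yet know which rule applies.

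At stake is the completeness of the AE and SAE tables (8.2.3.4.3 to 8.2.3.4.5) for patients whose toxicity was long enough to end treatment. From day 31 two kinds of event have no collection rule:

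- new non-serious AEs, even if related and even if grade 3 or 4, because 7.2.1 has no counterpart to the exception in 15.6;
- SAEs that the investigator judges unrelated. Whether an SAE is reported then turns on a causality judgement made in an open-label trial while the patient is still on protocol treatment.

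**Working it through.** The plan states neither the maximum wait nor a gap, so there is no figure to reproduce. The check is interval arithmetic, with the day of the last infusion as day 0.

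**Inputs**
- Cycle length, trabectedin: 21 days (chapter 4).
- Maximum delay past the due date: 3 weeks = 21 days (5.6.1.2, 5.6.1.3).
- Collection window after the last dose: 30 days (7.2.1, 15.6).

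**Maximum wait on protocol treatment:** 21 + 21 = 42 days.

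**Uncovered days** for a delay of d days with no further dose: max(0, 21 + d - 30).

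| Delay d (days) | Days since last dose | Uncovered days |
|---|---|---|
| 0 | 21 | 0 |
| 7 | 28 | 0 |
| 9 | 30 | 0 |
| 10 | 31 | 1 |
| 14 | 35 | 5 |
| 21 | 42 | 12 |

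The gap opens once the delay exceeds 9 days. At its largest it is 42 - 30 = 12 days (days 31 to 42), which is 12/42 = 29% of the interval. If the patient is re-dosed by day 42, the window runs from the new dose and the gap is 0.

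**What is covered on days 31 to 42 if no further dose is given**

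| Event | Covered? | Source |
|---|---|---|
| SAE judged related | Yes, no end date | 15.6 |
| AE already ongoing, including the toxicity behind the delay | Yes, to resolution or stabilization | 7.2.1, 6.4.1, 6.4.3 |
| SAE judged unrelated | No | 15.6 |
| New non-serious AE, related or not | No | 7.2.1 |

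**Do other sections close the gap?** The assessment of all new events in 6.3 is tied to day 1 of a cycle, and a patient who is never re-dosed has no further day 1. The text of 6.4.1 and 6.4.3 covers ongoing events only, and the 6.4.1 visit at day 30 can fall due before the off-treatment decision. Sections 6.5 and 8.2.3.4 presuppose some later AE assessment, but neither changes the end date in 7.2.1. They conflict with it.

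**Control arm.** Chapter 6 gives cycles of 3 or 4 weeks and no section gives a delay limit, so no maximum wait can be computed. For a 4-week cycle, day 30 is 30 - 28 = 2 days after the next cycle is due. That shows little slack, not a gap of known size.

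**The case against.** The strongest defence is that little is lost. A reader might infer that SAE collection simply stops at day 30. It does not: 15.6 keeps every SAE judged related reportable without an end date. A patient waiting under 5.6.1.2 has, by definition, a toxicity that began earlier, and 7.2.1 follows it to resolution or stabilization. The persistent toxicity itself is therefore recorded. Both points stand, and they confine the gap to the two kinds of event named above.

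A reader might also infer that events are recorded and then lost, so that the safety tables and periodic reviews under-count these patients. The documents do not show that. SAEs must be reported within 24 hours, usually before anyone knows that no dose will follow, and nothing tells sites to withdraw such reports. Section 8.2.3.4 does not cut its forms at day 30. The safety analysis is descriptive, without p-values or confidence intervals. Relative to the last dose, every patient has the same 30-day window unless new therapy starts sooner. Under-counting is possible but not established. What remains is that the text does not say whether events recorded while waiting are kept, and that 7.2.1 does not ask for new non-serious ones after day 30.

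Finally, one might put a number on the patients affected. If 10% to 20% of the 57 trabectedin patients stopped through the delay rule, that would be 57 x 0.10 = 5.7 to 57 x 0.20 = 11.4, or about 6 to 11. The rate is an assumption with no basis in the documents, and the result counts patients who could meet the gap, not events missed. Section 5.5 also allows withdrawal earlier than day 42 for toxicity or by investigator decision, so 12 days is a maximum.

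**Conclusion.** The point holds in a narrow form and is of minor severity. In trabectedin patients delayed more than 9 days and then taken off without another dose, up to 12 days on protocol treatment fall outside the window for new non-serious AEs (including related ones) and for SAEs judged unrelated. Related SAEs and AEs already ongoing remain captured. Section 7.2.1 also conflicts with 8.2.3.4, which expects severe grades that first appear in follow-up, and with the 6.5 table, which schedules AE assessment every 9 weeks until progression.

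The 12 days rest only on the stated cycle length, delay limit and window, and assume that the full delay is used and no new antitumor therapy starts meanwhile. The number of patients affected cannot be derived from the documents. No control-arm gap can be quantified. Neither a complete stop of SAE collection nor a demonstrated bias in the safety tables is supported.

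**What to change.** - In 7.2.1 and 15.6 (text and table row), end collection at the later of 30 days after the last dose and the date the patient is taken off protocol treatment. Apply this in both arms and keep the cut at the start of new antitumor therapy. The uncovered days on protocol treatment then fall from at most 12 to 0, unless new therapy starts first.
- Reconcile 7.2.1 with 8.2.3.4 and the 6.5 table: state whether new AEs with onset after the window are recorded, and whether related non-serious ones are treated as 15.6 treats related SAEs.
- Reconcile the timing of the 6.4.1 visit with 5.6.1.2 and 5.6.1.3, since day 30 can pass before the off-treatment decision.

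The delay and discontinuation rules are not affected.

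The cost is a wording change in two sections and one table row, the two reconciliations, and a few more days of AE recording in delayed patients who are not re-dosed. Collection windows may also differ somewhat in length between patients and between arms, because a delay limit is stated only for trabectedin. The descriptive safety tables should note this.

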15.7 Reporting responsibilities for EORTC

The EORTC Pharmacovigilance Unit will forward all SAE reports to the appropriate persons within the EORTC Headquarters and to the pharmacovigilance contact at the pharmaceutical company.

The EORTC Pharmacovigilance Unit will provide a six-monthly summary which will be added in the Trial Status Report and which will be accessible to all participating investigators.

The EORTC Pharmacovigilance Unit will take in charge the reporting of SUSARs/unexpected events to the Competent Authorities, Ethics committees, EudraVigilance Clinical Trial Module (EVCTM) and all participating investigators whenever applicable, following the local and international regulatory requirements.

15.8 Pregnancy reporting

Pregnancy occurring during a patient's participation in this trial, although not considered an SAE, must be notified to the EORTC Pharmacovigilance Unit within the same timelines as an SAE (within 24 hours) on a Pregnancy Notification Form. The outcome of a pregnancy should be followed up carefully and any adverse outcome to the mother or the child should be reported. This also applies to pregnancies in female partners of a male patient participating in this trial.

- ◆ Any pregnancy in a female patient diagnosed during the treatment period or within 3 months thereafter or in a female partner of a male patient diagnosed during the treatment period or within 5 months thereafter, must be reported to the EORTC Pharmacovigilance Unit
- ◆ This must be reported within 24 hours of first becoming aware of the event by fax, to the Pharmacovigilance Unit on a Pregnancy Notification Form
- ◆ If a SAE occurs in conjunction with the pregnancy, please also complete an SAE form as explained in the SAE reporting chapter
- ◆ All neonatal deaths that occur within 30 days of birth should be reported, regardless to the causality, as SAEs. In addition, any infant death at any time thereafter that the Investigator suspects to be related to the exposure to the study drug/IMP should also be reported to the Pharmacovigilance Unit by facsimile within 24 hours of the Investigator's knowledge of the event.

16 Quality assurance

16.1 Control of data consistency

Data forms will be entered in the EORTC Headquarters database by using the VISTA/RDC (Remote Data Capture) system. Computerized and manual consistency checks will be performed on newly entered forms; queries will be issued in case of inconsistencies. Consistent forms will be validated by the Data Manager. Inconsistent forms will be kept "pending" until resolution of the inconsistencies.

16.2 On-site quality control

The EORTC Headquarters will perform on-site quality control visits.

The first visit in a participating site will be performed within 6 months after the first patient's randomization at this site. Frequency and number of subsequent visits will depend on site's accrual and quality observed during the first visit.

Overall, the frequency of site visits will be around one visit a year per recruiting site.

The aim of these site visits will be:

- ◆ to verify that the site facilities remain adequate for performing the trial
- ◆ to verify that the principal investigator and site staff involved in the trial are working in compliance with GCP and protocol requirements
- ◆ to assess the consistency of data reported on the case report forms with the source data
- ◆ to check that Serious Adverse Events have been properly reported and that follow-up information or queries are correctly fulfilled
- ◆ to assist the site in resolving any outstanding queries
- ◆ to control the drug accountability process

